6.3. Method of Assigning Study Subjects to Treatment Groups (Randomization)

Each subject who meets all eligibility criteria, is accepted for the study, and signs an informed consent form will be randomized to receive mexiletine 300 mg/day or mexiletine 600 mg/day or placebo on a 1:1:1 basis. Randomization will be stratified by site and use of riluzole at screening.

The randomization scheme will be independently developed by the Biostatistics Center and will indicate the treatment assignment and the subject numbers to be used by each site. A programmer in the Biostatistics Center will develop the plan under the guidance of the chief biostatistician.

6.4. Study Drug Adjustments, Dosage Reductions and Suspensions

Any dosage adjustment including the reason for and dates of adjustment will be documented in the CRF for each subject requiring this manipulation. The Site Investigator or licensed physician Sub-Investigator has the option of reducing or temporarily stopping the study drug for AEs thought to be related to the study drug or any other reason during the trial (the reason for, and dates of suspension or dose reduction must be documented). If the adverse event is mild or moderate, the dosage may be reduced until the event improves (See Table 6. Study Drug Reduction Schedule). The Site Investigator may then choose to resume the higher dosage or maintain the subject at a reduced dosage. If the event is serious or life threatening, and deemed to be drug related, the study drug should be discontinued immediately. Study subjects may remain off the study drug permanently, until the condition improves or they may resume on a reduced dosage, as advised by the Site Investigator. Subjects may not resume study drug after a suspension that is longer than 10 days. Any resumption of drug after a suspension requires approval from the Medical Monitor. All adverse events will be followed for resolution or 28+5 days after stopping study drug.

Table 6. Study Drug Reduction Schedule: Number of capsules per bottle per day

	Day 1-2 Dose Reduction	Day 3-4 Dose Reduction	Day 5-6 Dose Reduction
Bottle #1	1 BID	1 BID	1 Q AM
Bottle #2	1 Q AM	-	-

6.4.4. Dosage Re-Challenge

The Site Investigator or licensed physician Sub-Investigator may choose to re-challenge a subject after approval from the Medical Monitor if the adverse event resolves or it is felt that the study subject can continue safely. Subjects may not resume study drug after a suspension that is longer than 10 days.

6.4.5. Dosage Discontinuation

Reasons for discontinuation of study medication may include an adverse event, Medical Monitor or Site Investigator recommendation, Sponsor termination, protocol violation, loss to follow-up, patient request, or death. All serious adverse events (SAEs) that occur in a subject who has terminated early must be recorded and reported within 24 hours of awareness.

Study subjects who discontinue study drug prematurely should remain on study as described in Section 5.5.

6.5. Blinding

The Randomization ID will be used to identify the subject's electronic case report forms (eCRFs), laboratory tests, study medication and all communications. Study Subjects, Investigators, Coordinators, Clinical Evaluators (and all other study site staff), Study Monitors, Project Management, Clinical Laboratory and Data Management personnel, and the Sponsor will be blinded to treatment group assignment throughout the study. Only the Biostatistician developing the randomization schedule, the Research Pharmacists at the Central Pharmacy and the Site Pharmacist storing and distributing the study drug at each site will be unblinded to the individual drug assignments in this study.

6.5.1. Emergency Unblinding

An emergency unblinding procedure will allow the Site Investigator the option of learning the treatment assignment for an individual subject if clinical circumstances require it. For unblinding, the Site Investigator must contact the Medical Monitor. The Site Investigator should attempt to contact the NCRI Coordination Center prior to completing emergency unblinding if time allows. If this is not possible, the site must inform the NCRI Coordination Center as soon as possible regarding the emergency unblinding and the circumstances surrounding it. The Site Investigator must document the reason for unblinding in the subject's source documents.

Rarely should such an extreme action be taken. Experimental medications can usually be withdrawn without the need for unblinding. Sites should take care to unblind only those study staff member(s) and other persons whose knowledge of the treatment assignment is necessary for the clinical safety of the subject. Sites should take all reasonable measures to keep study staff, NCRI Coordination Center staff and the subject blinded to treatment assignment, especially site staff completing any Early Termination Visit procedures, if possible.

In the event that emergency disclosure of treatment assignment is necessary, the study subject will be withdrawn from further participation in the trial. All adverse events (AEs) resulting in emergency unblinding will be followed for resolution.

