5.5. Reasons for Withdrawal

A subject will be withdrawn from the study if:

- Any clinical AE, laboratory abnormality, concurrent illness, or other medical condition or situation occurs such that continued participation in the study would not be in the best

interest of the subject. Note, however, that any subject who has initiated treatment should only discontinue study drug and remain on study if the safety concern relates to study drug and not to study procedures.

- The subject no longer meets eligibility criteria at any time prior to initiating study drug or is discovered at anytime to have been enrolled in error.

Subjects are free to withdraw from participation in the study at any time upon request.

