5.6. Handling of Withdrawals

The medical monitor should be notified in all instances a subject may choose to discontinue their participation, start a prohibited medication, or wishes to withdraw consent.

A subject may choose to discontinue participation in the study at any time. However, the SI or designee will encourage subjects to continue with follow-up, regardless of their compliance with study drug. If a subject who initiated study drug permanently discontinues study drug, the SI or designee should still encourage subjects to follow the study protocol under the modified intent-to-treat principle (ITT). Subjects unable or unwilling to return for clinic visits should be encouraged to receive follow-up telephone calls per the study visit schedule up to Week 8. These calls will include administration of the ALSFRS-R and review of adverse events and concomitant medications. Loss to follow-up should be prevented whenever possible

Any subject who is on study drug and needs to begin the use of any prohibited medication, must immediately discontinue use of study drug and should not begin use of the prohibited medication before an appropriate wash-out period occurs. Subjects who permanently discontinue study drug should return any unused study drug and complete early study drug discontinuation procedures without any study drug unblinding, if possible. Subjects who must permanently discontinue study drug may continue in the ITT portion of the study, per protocol.

If a subject wishes to withdraw consent, i.e., withdraw his or her participation in future study procedures, the subject will be asked to delay consent withdrawal to allow for a final safety visit and final safety telephone call. The subject will be asked to return to the study site for a final safety visit within 14 days of asking to withdraw consent. The subject will also be asked to have a final telephone call no sooner than 28 days after taking their last dose of study drug to monitor their safety and to permit review of their medical records at the end of the study to document their vital status.

Subjects who discontinue study drug due to an AE will be followed for outcome measures under the ITT protocol as noted above.

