13.4. Missing Data

The trial will be intent-to-treat. We will get follow-up outcome measure information for all subjects whether or not they continue on treatment. If a subject is lost to follow-up, their data will be included in the primary analysis. Data from unobserved visits will be assumed missing at random conditional on the observed visits. If loss to follow-up appears to be associated with treatment arm, then sensitivity analyses will be pursued to investigate the possible influence of non-ignorable missingness.

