log. However, if an observed or reported sign, symptom, or clinically significant laboratory anomaly is not considered by the SI to be a component of a specific disease or syndrome, then it should be recorded as a separate AE on the AE log. Clinically significant laboratory abnormalities, such as those that require intervention, are those that are identified as such by the SI.

Subjects will be monitored for AEs from the time they sign consent until completion of their participation in the study (defined as death, consent withdrawal, loss to follow up, early study termination for other reasons or following completion of the entire study).

An unexpected AE is any AE, the specificity or severity of which is not consistent with the current IB. An unexpected, suspected ADR is any unexpected AE that, in the opinion of the SI or Sponsor, there is a reasonable possibility that the investigational product caused the event.

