2.4 Participant Flow

After a site is activated for recruitment of ALS participants and after each ALS patient provides informed consent and is determined eligible, approximately 60 participants will be randomized to receive placebo, 300 mg/day oral mexiletine, or 600 mg/day oral mexiletine in a 1:1:1 ratio, stratified by clinical site and use of riluzole at screening. Participants are first dose of study drug is administered at the baseline visit and are intended to remain on study drug for 4 weeks. After baseline, participants receive a telephone call at week 1 and complete in-clinic evaluations at weeks 4 and 8. Participants who discontinue study drug should remain on study following the normal schedule of assessments. Patients withdrawing consent are asked to delay withdrawing consent until after they return for a Final Safety Visit within 2 weeks after their last dose of study drug and after they complete a final telephone call 4 weeks after their last dose of study drug.

Detailed descriptions of study procedures and timing are specified in the clinical protocol.

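### Protocol 6.5.1 ends trial participation after emergency unblinding, which conflicts with the follow-up promised in Protocol 5.5, 5.6 and 13.4 and SAP 2.4

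*Protocol*

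**What the plan says.** Protocol 6.5.1 lets the Site Investigator learn a patient's assignment when clinical circumstances require it, and then directs: "In the event that emergency disclosure of treatment assignment is necessary, the study subject will be withdrawn from further participation in the trial". The next sentence adds: "All adverse events (AEs) resulting in emergency unblinding will be followed for resolution". The section expects the event to be uncommon: "Rarely should such an extreme action be taken".

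Elsewhere the plan keeps dosed patients in follow-up:

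- Protocol 5.5: "any subject who has initiated treatment should only discontinue study drug and remain on study if the safety concern relates to study drug". Its list of reasons for withdrawal does not mention unblinding.
- Protocol 5.6: "Subjects who discontinue study drug due to an AE will be followed for outcome measures under the ITT protocol as noted above".
- Protocol 6.4.5 sends patients who stop study drug early back to 5.5.
- Protocol 13.4: "We will get follow-up outcome measure information for all subjects whether or not they continue on treatment".
- SAP 2.4: "Participants who discontinue study drug should remain on study following the normal schedule of assessments".

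On adverse events, Protocol 14.1.1 says: "Subjects will be monitored for AEs from the time they sign consent until completion of their participation in the study". It counts early study termination as one way in which participation is completed.

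**The concern.** A patient whose code is broken because of a drug-related event falls under two instructions. One ends participation; the other stops the drug at most and continues the visits. A site cannot follow both.

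If 6.5.1 prevails, the trial creates missing data by its own rule, in patients selected by what happened to them clinically. The intent-to-treat commitment is then not met for them. The missing-at-random assumption in Protocol 13.4 conditions on the observed visits, not on the event that led to removal. Scheduled safety collection also ends early for these patients.

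Knowing the assignment does not prevent anyone from measuring RMT, an ECG or a laboratory value. Protocol 6.5.1 itself asks that unblinding be confined to those who need to know.

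**Working it through.** **1. Is there an exemption?** None was found in Protocol 5.5, 5.6, 6.4.5, 8.1.7 or 13.4, or in SAP 2.4 or 3.5. Protocol 5.6 even foresees that stopping drug may involve unblinding (it asks sites to avoid this where possible), and still allows such patients to continue in the ITT portion. The SAP introduction gives the SAP authority on analysis and the protocol authority on everything else. This is a question of conduct, so the protocol governs, and the protocol contradicts itself.

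**2. What is lost and what is kept?**

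| | If 6.5.1 applies | What remains |
|---|---|---|
| Unblinded before the Week 4 visit | Week 4 and Week 8 visits | One requested Final Safety Visit with TMS (Protocol Study Workflow, 8.1.7): at most one of two post-baseline RMT values |
| Unblinded between Week 4 and Week 8 | Week 8 visit | The Week 4 RMT value. The Study Workflow asks for a Final Safety Visit; SAP 2.8 footnote 12 confines it to patients who stop drug before Week 4 |
| Known adverse events | – | Followed to resolution or 28+5 days after stopping drug (6.4); the triggering event to resolution (6.5.1) |
| New SAEs | Scheduled enquiry | Reported on awareness (6.4.5) |
| New non-serious events, ECG and laboratory changes | Scheduled collection after the Final Safety Visit | None scheduled. The final call at 28 days or later in 5.6 is written for consent withdrawal |

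SAP 3.7.1 assigns Final Safety Visit data to the closest scheduled post-baseline visit. With TMS visits targeted at 29 and 56 days (Protocol Table 7), the midpoint is (29 + 56)/2 = 42.5. Any such visit up to Day 42 is therefore analysed as Week 4, the primary time point, even if it took place in the second or third week.

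**3. Size in power terms.** Inputs from Protocol 13.9 and SAP 3.4: SD 5.1%, difference 5.3%, two-sided alpha 0.027, 60 randomized 1:1:1, 10% loss. That leaves 20 × 0.9 = 18 per arm.

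- Standard error = 5.1 × √(1/18 + 1/18) = 1.700; noncentrality = 5.3/1.700 = 3.118; degrees of freedom = 54 − 3 = 51; critical t = 2.277.
- Power = 79.7% (noncentral t). The normal approximation, Φ(3.118 − 2.212), gives 81.8%. The plan's 80% is reproduced.

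Now assume k further losses in one active arm, with noncentrality 5.3/[5.1 × √(1/18 + 1/(18 − k))]:

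| k | Noncentrality | df | Power for that dose |
|---|---|---|---|
| 0 | 3.118 | 51 | 79.7% |
| 1 | 3.073 | 50 | 78.4% |
| 2 | 3.025 | 49 | 76.9% |
| 3 | 2.973 | 48 | 75.3% |

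The SAP's primary comparison pools the two doses at alpha 0.05. If both doses had the 5.3% effect, noncentrality = 5.3/[5.1 × √(1/18 + 1/36)] = 3.600 and power is 94.2%. One or two losses reduce it to 94.0% or 93.8%.

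**4. Would the missing-data plan react?** SAP 3.7.7 says sensitivity analyses may be pursued if more than 20% of participants lack follow-up data. Of 60, that means more than 12 patients. One to three are 1.7% to 5.0%, so these losses alone would not trigger it.

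**The case against.** The best defence is that 6.5.1 is a specific rule for a rare event, whereas 5.5, 5.6 and 8.1.7 concern stopping study drug, and that the loss is small because safeguards remain. Much of this stands:

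- Follow-up does not simply stop. The provisions of 6.4, 6.4.5 and 6.5.1 in the table above are real, and 6.5.1 itself refers to Early Termination Visit procedures.
- A patient unblinded before Week 4 who attends the Final Safety Visit contributes a post-baseline RMT. One unblinded after Week 4 already has the primary value. A reader might infer that both values are lost; that requires the patient also to miss the requested visit.
- A reader might infer that the patients with the worst safety events are the ones removed, or that the losses will fall in the active arms. The documents say neither. The trigger is clinical need, and 6.5.1 notes that drug can usually be withdrawn without breaking the code.
- A reader might infer that the 10% loss allowance would be used up. That needs two unblindings in one arm of 20; two patients are 3.3% of 60, and nothing in the documents gives that rate. In the earlier ALS trial (Protocol 2.1.3.2 and Table 4), one SAE was reported among 20 + 19 = 39 patients on active drug, over 12 weeks and at up to 900 mg/day.
- Protocol 13.4 does foresee sensitivity analyses if loss appears related to arm.

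The specific-rule argument does not remove the conflict. The promise in 13.4 covers all subjects, and 5.5 covers any treated patient with a drug-related safety concern, which is a plausible reason to break the code. The safeguards also do not replace the scheduled visits: one early visit cannot stand in for both Week 4 and Week 8.

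**Conclusion.** The contradiction is established from the text. Protocol 6.5.1 conflicts with 13.4 in every case, and with 5.5, 5.6, 6.4.5 and SAP 2.4 where the unblinding follows a drug-related safety concern.

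The consequence is moderate and partly offset. Per affected patient it is the loss of one or two scheduled visits and of scheduled collection of new non-serious findings, with the possibility that an early off-schedule RMT is analysed as Week 4. On power the effect is small: about 1.3 to 4.4 percentage points for a single dose, assuming one to three losses in one active arm beyond the planned 10%. That assumption is ours, since the documents give no unblinding rate. The stated 80% power is not in error.

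The reason to act is that the missing data are avoidable and depend on safety events, in arms of about 20. The change should be made, but the trial's validity does not turn on it.

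**What to change.** Reconcile 6.5.1 with Protocol 5.5, 5.6 and 13.4 and SAP 2.4 by replacing the withdrawal sentence with a statement on follow-up only:

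- Emergency unblinding does not by itself end study follow-up. The patient is asked to complete the remaining scheduled visits and adverse event collection.
- The patient stays in the mITT and Safety and Tolerability samples.
- TMS and TTNCS are done, where possible, by a physiologist who has not been told the assignment.
- Self-reported outcomes collected after unblinding are flagged as potentially unblinded.

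The cost is a short protocol edit. Protocol 7.2.1 already allows up to two TMS and two TTNCS physiologists per site, although a change of physiologist departs from its preference for the same one throughout. The downside is that later reports from an unblinded patient (cramps, ALSFRS-R) may no longer be blind.

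Whether study drug stops after unblinding is a clinical rule that the sponsor must reconcile separately with 6.4 and 6.4.5; none is proposed here. The change should not be extended to patients found to have been enrolled in error: SAP 3.5 limits both samples to eligible participants, so that is a different question.

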6.6. Excluded, Prior and Concomitant Medications

Throughout the study, Site Investigators or licensed physician Sub-Investigators may prescribe concomitant medications or treatments deemed necessary to provide adequate supportive care provided that the medications are licensed in the US and not prohibited.

Study subjects should not receive other experimental therapy during the study. This includes marketed agents at experimental dosages that are being tested for the treatment of ALS. Subjects and/or primary caregivers should consult with the site Principal Investigator or licensed physician Sub-Investigator prior to initiating any new medication, including non-prescription compounds or any other non-drug therapy.

The following medications are prohibited when given on an as needed (PRN) basis. A subject must therefore be on a stable dose for 30 days prior to the Screening Visit, and the dose must not change during the course of the study, unless there is a safety risk to the subject, in which case the change must be documented at the subsequent clinical encounter.

* Benzodiazepines

- * Muscle relaxants
- * Tricyclic antidepressants
- * Selective serotonin reuptake inhibitors
- * Non-selective serotonin reuptake inhibitors
- * Sedating antihistamines including the following:
 - Alimemazine
 - Chlorphenamine
 - Clemastine
 - Cyproheptadine
 - Hydroxyzine
 - Ketotifen
 - Promethazine
- * Anti-cholinergics.

Any investigational therapy being used or evaluated for the treatment of ALS is prohibited beginning 30 days prior to Screening Visit and throughout the study. This includes, but is not limited to, the following:

- Pioglitazone
- Arimoclomol
- Olanzapine
- Tamoxifen
- Mexiletine
- NP001
- Ezogabine (Retigabine)
- Tocilizumab (Actemra)
- Tirasemtiv
- Ibudilast
- Fingolimod
- Ozanezumab (GSK 1223249)
- Rasagiline
- Memantine
- CK-2017357
- CK-2127107
- RNS60 (Revalesio)
- Masitinib
- Immune Modulating Treatments
- Anti-sense oligonucleotide (ASO) or other gene experimental therapies targeting SOD1 or C9orf72

The Site Investigator should contact the medical monitor with any questions regarding prohibited concomitant medication usage.

6.6.1. Drug Interactions

Due to increased risk of prolonged QT and cardiac arrhythmias, study subjects will not be able to take concomitantly the anti-arrhythmics amiodarone and flecainide. The use of duloxetine,

tizanidine, and clozapine will also be prohibited in this study due to their ability to inhibit hepatic metabolism and alter mexiletine levels. Site investigators should contact the medical monitor for concerns about potential interactions with other medications.

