2.2.1. Pharmacokinetics

2.2.1.1. Absorption, Distribution, Elimination and Metabolism

Mexiletine is well absorbed (~90%) from the gastrointestinal tract. Unlike lidocaine, its first-pass metabolism is low. Peak blood levels are reached in two to three hours. In normal subjects, the plasma elimination half-life of mexiletine is approximately 10 to 12 hours. It is 50 to 60% bound to plasma protein, with a volume of distribution of 5 to 7 liters/kg. Mexiletine is mainly metabolized in the liver, the primary pathway being CYP2D6 metabolism, although it is also a substrate for CYP1A2. With involvement of CYP2D6, there can be either poor or extensive metabolizer phenotypes. Since approximately 90% of mexiletine hydrochloride is metabolized in the liver into inactive metabolites, pathological changes in the liver can restrict hepatic clearance of mexiletine hydrochloride and its metabolites. The metabolic degradation proceeds via various pathways including aromatic and aliphatic hydroxylation, dealkylation, deamination and N-oxidation. Several of the resulting metabolites are submitted to further conjugation with glucuronic acid (phase II metabolism); among these are the major metabolites p-hydroxymexiletine, hydroxy-methylmexiletine and N-hydroxy-mexiletine. Approximately 10%

is excreted unchanged by the kidney. While urinary pH does not normally have much influence on elimination, marked changes in urinary pH influence the rate of excretion: acidification accelerates excretion, while alkalinization retards it.

Several metabolites of mexiletine have shown minimal antiarrhythmics activity in animal models. The most active is the minor metabolite N-methylmexiletine, which is less than 20% as potent as mexiletine. The urinary excretion of N-methylmexiletine in man is less than 0.5%. Thus the therapeutic activity of mexiletine is due to the parent compound.

Hepatic impairment prolongs the elimination half-life of mexiletine. In eight patients with moderate to severe liver disease, the mean half-life was approximately 25 hours.

Consistent with the limited renal elimination of mexiletine, little change in the half-life has been detected in patients with reduced renal function. In eight patients with creatinine clearance less than 10 mL/min, the mean plasma elimination half-life was 15.7 hours; in seven patients with creatinine clearance between 11 to 40 mL/min, the mean half-life was 13.4 hours.

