2.2.2. Drug Interactions

Since mexiletine hydrochloride is a substrate for the metabolic pathways involving CYP2D6 and CYP1A2 enzymes, inhibition or induction of either of these enzymes would be expected to alter mexiletine plasma concentrations. In a formal, single-dose interaction study (n = 6 males) the clearance of mexiletine was decreased by 38% following the coadministration of fluvoxamine, an inhibitor of CYP1A2. In another formal study (n = 8 extensive and n = 7 poor metabolizers of CYP2D6), coadministration of propafenone did not alter the kinetics of mexiletine in the poor CYP2D6 metabolizer group. However, the metabolic clearance of mexiletine in the extensive metabolizer phenotype decreased by about 70% making the poor and extensive metabolizer groups indistinguishable. In this crossover steady-state study, the pharmacokinetics of propafenone were unaffected in either phenotype by the coadministration of mexiletine. Addition of mexiletine to propafenone did not lead to further electrocardiographic parameters changes of QRS, QTc, RR, and PR intervals than propafenone alone. When concomitant administration of

either of these two drugs is initiated, the dose of mexiletine should be slowly titrated to desired effect.

In a large compassionate-use program, mexiletine has been used concurrently with commonly employed antianginal, antihypertensive, and anticoagulant drugs without observed interactions. A variety of antiarrhythmics such as quinidine or propranolol were also added, sometimes with improved control of ventricular ectopy. When phenytoin or other hepatic enzyme inducers such as rifampin and phenobarbital have been taken concurrently with mexiletine, lowered mexiletine plasma levels have been reported. Monitoring of mexiletine plasma levels is recommended during such concurrent use to avoid ineffective therapy.

In a formal study, benzodiazepines were shown not to affect mexiletine plasma concentrations. ECG intervals (PR, QRS, and QT) were not affected by concurrent mexiletine and digoxin, diuretics, or propranolol.

Concurrent administration of cimetidine and mexiletine has been reported to increase, decrease, or leave unchanged mexiletine plasma levels; therefore patients should be followed carefully during concurrent therapy.

Mexiletine does not alter serum digoxin levels but magnesium-aluminum hydroxide, when used to treat gastrointestinal symptoms due to mexiletine, has been reported to lower serum digoxin levels.

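### Exclusion 12 and Protocol 6.6.1 bar three drugs for altering mexiletine levels but omit fluvoxamine, for which Protocol 2.2.2 itself reports 38% lower mexiletine clearance

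*Protocol*

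**What the plan says.** Protocol 6.6.1 gives two reasons for barring drugs. Amiodarone and flecainide are barred for QT and arrhythmia risk. Duloxetine, tizanidine and clozapine "will also be prohibited in this study due to their ability to inhibit hepatic metabolism and alter mexiletine levels". Exclusion 12 lists the same five drugs. For any other medication, 6.6.1 refers interaction concerns to the medical monitor.

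Protocol 2.2.2 attaches a figure for reduced mexiletine clearance to only two drugs:

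- **Fluvoxamine:** "the clearance of mexiletine was decreased by 38% following the coadministration of fluvoxamine, an inhibitor of CYP1A2". This was a single-dose study in 6 males.
- **Propafenone:** "the metabolic clearance of mexiletine in the extensive metabolizer phenotype decreased by about 70" percent, "making the poor and extensive metabolizer groups indistinguishable". Poor metabolizers were unchanged.

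When either drug is combined with mexiletine, 2.2.2 advises that "the dose of mexiletine should be slowly titrated to desired effect". Neither drug appears in exclusion 12, 6.6 or 6.6.1.

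Section 6.6 lets investigators prescribe any US-licensed drug that is not prohibited. Inclusion 13 and 6.6 admit selective serotonin reuptake inhibitors (SSRIs) as a class, provided the dose is scheduled and has been fixed for 30 days before screening.

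**The concern.** The sponsor chose outright prohibition for three drugs on a stated ground, yet did not apply it to a drug that meets the same ground and has a figure in the protocol's own background. None of the three barred drugs has such a figure anywhere in the documents.

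What is at stake is tolerability, and safety to a lesser degree. The 600 mg/day dose was chosen because 900 mg/day was not tolerable in the earlier ALS trial, where Section 2.1.3.2 reports 32% intolerance against 5% at 300 mg/day. A fluvoxamine user assigned to 600 mg/day would have average exposure close to that of 900 mg/day.

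An avoidable interaction could then be recorded as intolerance of 600 mg/day. Protocol 7.1.6 treats any dose reduction as intolerance. SAP 3.2.4 counts failure to reach the target dose or to stay on drug. Protocol 13.8 uses tolerability to choose the dose for future trials.

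**Working it through.** The plan gives no figure of its own to reproduce, so the check has two parts: whether the text leaves fluvoxamine open, and how large the effect would be.

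**Text.** Fluvoxamine is named only in 2.2.2. The default rule in 6.6 therefore permits it. Subjects must consult the investigator before starting a new drug, but that does not reach a drug already taken at screening. Referral to the medical monitor depends on the site recognising a problem. The escalation in 6.2.1 is fixed, blinded and complete by Day 7; it is not titration to effect.

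**Inputs for size.**
- Clearance falls by 38% with fluvoxamine (2.2.2).
- Hepatic share: "approximately 90% of mexiletine hydrochloride is metabolized in the liver into inactive metabolites" (2.2.1.1).
- Half-life: "the plasma elimination half-life of mexiletine is approximately 10 to 12 hours"; peak: "Peak blood levels are reached in two to three hours" (2.2.1.1).
- Twice-daily dosing (6.2).
- Mean 2-hour levels in the earlier trial: 0.4 µg/mL at 300 mg/day and 1.27 µg/mL at 900 mg/day (2.1.3.2). The ratio is 1.27/0.4 = 3.2 for a 3-fold dose, so linear kinetics are a fair approximation.

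**Average exposure = dose/clearance.** The remaining clearance fraction f is 0.10 + 0.90 × 0.62 = 0.658 if only the hepatic 90% falls, and 0.62 if total clearance falls. The exposure ratio is 1/0.658 = 1.52 to 1/0.62 = 1.61.
- 600 mg/day: 600/0.658 = 912 to 600/0.62 = 968 mg/day equivalent.
- 300 mg/day: 300/0.658 = 456 to 300/0.62 = 484 mg/day equivalent, below the 600 mg/day target.

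**2-hour level.** A one-compartment oral model at steady state makes the level proportional to dose × S, where

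S(ke, τ) = ka/(ka − ke) × [exp(−2ke)/(1 − exp(−τke)) − exp(−2ka)/(1 − exp(−τka))].

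Here τ is the dosing interval and ke = ln2/half-life, for 10, 11 and 12 h. ka solves ln(ka/ke)/(ka − ke) = time to peak, for 2, 2.5 and 3 h. Inhibition replaces ke by f × ke, with volume and ka unchanged.

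*If the earlier trial also dosed twice daily.* The level at 600 mg/day without inhibitor is 0.4 × 600/300 = 0.80 to 1.27 × 600/900 = 0.847.
- f = 0.658: ratio 1.394 to 1.424, level 0.80 × 1.394 = 1.12 to 0.847 × 1.424 = 1.21.
- f = 0.62: ratio 1.465 to 1.501, level 0.80 × 1.465 = 1.17 to 0.847 × 1.501 = 1.27.

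*If the earlier trial dosed three times daily.* Then 900 mg/day is 300 mg per dose, the same unit dose as 600 mg/day given twice daily, so the level is 1.27 × S(f·ke, 12)/S(ke, 8).
- f = 0.658: 1.31 to 1.33.
- f = 0.62: 1.38 to 1.39.
- Scaling from the 300 mg/day arm instead (0.4 × 3 × the same ratio) gives 1.24 to 1.32.

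Overall the 2-hour level is about 1.1 to 1.4 µg/mL.

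**Propafenone.** Here f = 0.10 + 0.90 × 0.30 = 0.37 if metabolic clearance falls by 70%, and 0.30 if total clearance does.
- 600 mg/day: 600/0.37 = 1622 to 600/0.30 = 2000 mg/day equivalent.
- 300 mg/day: 300/0.37 = 811 to 300/0.30 = 1000 mg/day equivalent.

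Both active arms would be affected.

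**Number affected.** The documents give no rate of use. At an assumed 1% to 5%, 20 × 0.01 = 0.2 to 20 × 0.05 = 1 patient in the 600 mg/day arm.

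**The case against.** The strongest case on the other side is that 6.6.1 is a list of named drugs with a referral route, not a rule that every inhibitor is barred. Section 2.2.2 advises slow titration with fluvoxamine, not avoidance. It also mentions cimetidine and enzyme inducers, which are not barred either. Poor CYP2D6 metabolizers are enrolled without restriction, and their clearance is evidently further from normal than 38%.

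Other safeguards exist: medication review at screening and before the first dose, post-dose observation and ECG, the Week 1 call, dose reduction, a Week 4 plasma level and an analysis by achieved level. Even the full gap of 32% − 5% = 27 points applied to 0.2 to 1 patient gives only 0.05 to 0.27 extra intolerant patients. The ban would turn away 90 × 0.01 = 0.9 to 90 × 0.05 = 4.5 of about 90 screened.

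Most of this stands as a limit on size. It is right that the documents state no general rule against inhibitors, and a reader should not infer one. It does not remove the inconsistency. The sponsor had already accepted the cost of exclusion for three drugs with the same stated mechanism, and metabolizer status is not a choice of co-medication that a protocol can simply rule out. None of the safeguards stops a stable user from being escalated to full dose; most act only after exposure.

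**Conclusion.** The omission is real and minor. Fluvoxamine meets the stated ground for prohibition, is permitted by default, and would bring a 600 mg/day patient to roughly the average exposure of 912 to 968 mg/day. This rests on linear kinetics and on a 38% figure from a single-dose study in 6 males holding at steady state, so the equivalents are indicative.

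Five stronger readings are not supported:

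- **Toxic levels with fluvoxamine.** The estimated mean 2-hour level of 1.1 to 1.4 µg/mL stays inside the 0.5 to 2.0 range in 2.2.1.1, and the earlier trial found 900 mg/day safe, though poorly tolerated.
- **A 2-hour level no higher than that seen at 900 mg/day.** This holds only if the earlier trial dosed twice daily. The documents do not give its interval; with three-times-daily dosing the estimate is 1.24 to 1.39 against 1.27.
- **Only the 600 mg/day arm matters.** That is reasonable for fluvoxamine but not for propafenone, which would raise 300 mg/day to the equivalent of 811 to 1000 mg/day. Propafenone is the lesser case only because exclusion 6 (known arrhythmia) should remove most users.
- **The protocol expressly admits fluvoxamine.** It admits the SSRI class. That fluvoxamine belongs to it is general pharmacology, not stated in the documents. The point stands on the default rule in 6.6.
- **A threat to the primary result.** With 0.2 to 1 affected patient at the assumed rates, the pooled comparison in SAP 3.7.1 is essentially unchanged.

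**What to change.** Add fluvoxamine to exclusion 12 and to the drugs prohibited in 6.6.1 for altering mexiletine levels. State in inclusion 13 and in 6.6 that the stable-dose allowance for SSRIs does not cover fluvoxamine. Propafenone may be added in the same two places for consistency.

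The wording change is one or two drug names in two places and one clause in two others. It still needs a small protocol amendment, with Coordination Center and then site IRB approval (Protocol 4.5) at about 9 sites. It may also exclude a few otherwise eligible patients, on the assumed use rates given above. Design, sample size and analysis do not change.
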